#### **4.1.2 Exclusion Criteria**

The following will be excluded from participation: (1) autologous and directed donors; these persons inherently have an altered risk profile that is different from allogeneic donors and consequently not generalizable; (2) deferred donors (3) donors less than age 18, prisoners, or participants otherwise unable to provide informed consent; (4) donors from whom insufficient volume of blood was collected to complete their virology testing, i.e. failed phlebotomies; and (5) donors with any other condition that, in the opinion of the Investigator of Record or his/ her designee, would preclude informed consent, make study participation unsafe, complicate interpretation of study outcome data, or otherwise interfere with achieving the study objectives.

## 4.2 Study Enrollment or Specimen Procurement

### 4.2.1 Screening/Recruitment/Specimen Acquisition

SANBS operations are divided into seven zones, covering eight of the nine provinces of South Africa. Each zone has a Medical Liaison Officer (MLO) who has the primary responsibility for managing donors who test positive for either HIV antibodies or HBV antigen, as well as donors who are antibody/antigen-negative but NAT-positive (NAT yields). Each unit of blood collected by SANBS is tested for HIV, HBV, Hepatitis C Virus (HCV) and syphilis. Donation testing results influence whether standard operational procedures for donor recall and retesting or study protocol procedures will be used. Testing is performed at two testing centres which are located in Constantia Kloof, Gauteng (Johannesburg area) and Pine Town in KwaZulu-Natal (Durban area). Serological assays for anti-HIV, anti-HCV and HBsAg using Abbott Prism are performed simultaneously with nucleic acid testing (NAT) using Ultrio Plus in individual testing format. Donations found repeat reactive by serology but NAT non-reactive or NAT non-repeatable reactive are confirmed using either an HIV Western Blot for HIV or an HBsAg neutralization assay for HBV. If these confirmatory tests are reactive then the donor is classified as a potential serology yield. Donations found negative by serology but repeat reactive by NAT testing are classified as a potential NAT yield. Confirmation of NAT yield status is achieved by assessing the following for HIV: seroconversion in a follow-up sample, detectable viral load, p24 antigen positive result or repeat reactivity on plasma from the fresh frozen plasma unit from the index donation ; and the following for HBV: seroconversion to either HBsAg or anti-HBc on follow up sample, anti-HBc reactivity on current sample, detection of viral load or repeat reactivity on plasma from the fresh frozen plasma unit from the index donation. Figures 1 and 2 provide detailed flow diagrams of the planned study activities for HIV and HBV positive donors, respectively.

Each positive donation is entered into a centralized database maintained at SANBS headquarters in Johannesburg (Constantia Kloof). Information pertaining to viral positive donations is forwarded to the regional MLO on a weekly basis through an automated report generated from the database. Basic demographic information for all recently acquired HIV and HBV infections identified at the point of index donation will be available to the study team so that we may evaluate the potential for non-response bias among those who are enrolled vs. not enrolled among those eligible.

[figure not shown]
The MLO, in cooperation with the research nurses who will be employed specifically for this study, will coordinate recall of the donors to the blood centre for follow-up counseling and testing. Initial contact with donors who have positive HIV or HBV test results consistent with recently acquired infection will be made as soon as possible after receiving the laboratory results reports. All NAT yield donors will, wherever possible, be contacted by a staff member

who speaks the donor's home language as the initial contact will be via telephone. During this telephone call, an appointment will be made for the donor to return for follow-up testing at a specific date, time and venue. If the donor cannot, after repeated attempts, be contacted via telephone, a first letter and text message will be sent to the donor. If the donor were to respond to the letter or text message, an appointment will be confirmed for that donor. Letters confirming the date, time and venue of the appointment will be sent to each donor and will be followed by a text message the day before the appointment. Where donors refuse to return to the blood centre for follow-up, they will be strongly urged to go to their preferred doctor or health care clinic to which the initial results will be made available. Study staff will systematically document all contact attempt methods, dates, and outcomes for all individuals with positive test results in a Contact Log.

When potential study participants return to the SANBS clinic for follow-up testing, collection of the follow-up samples for repeat testing and enrollment onto the study will be managed by a combination of the MLO and the research nurses. (The extent of the research questionnaire and the availability of laptops will preclude the use of SANBS collections staff to perform this function). Each donor will receive pre-test counseling. Wherever possible, follow-up appointments will be made for the donor to return for the final confirmatory results notification at this time.

The tests that will be performed as part of this study depend on SANBS standard testing procedures and results from the index donation. Based on whether a donor tests serology only positive, concordant serology and NAT, or NAT only positive different tests will be conducted on both the index donation residual specimen volumes that remain available and additional specimens that are collected at the time of returning to the blood centre. Tables 1 and 2 show the standard testing and REDS-III protocol testing that will be conducted.

Figure 1 Approaches for HIV-positive donor testing and study entry.

**Figure 2 Approaches for HBV-positive donor testing and study entry.**

[figure not shown]

Table 1 Planned HIV testing based on index donation test results.

Index Donation Testing Result	Tests to be Conducted on Index Donation Specimens	Tests to be Conducted on Follow-up Samples	SANBS Standard Procedure Testing	REDS-III Study Protocol Testing
Serology Only Positive	Serology confirmatory (Immunocomb)	NAT	X	
	Western Blot	Serology	X	
		Western blot	X	
NAT and Serology Concordant Positive	LAg Avidity	LAg Avidity (if no index sample available)		X
	Serology confirmatory (Immunocomb)			X
	Western Blot if LAg avidity negative			X
	p24 Ag if LAg avidity negative			X
	Viral Load if LAg avidity negative			X
	Genotyping if LAg avidity negative	Genotyping (in no index sample available)		X
	Drug resistance if LAg avidity negative	Drug resistance (if no index sample available)		X
		NAT confirmatory		
		Serology confirmatory		
		Viral load		X
		Western Blot if p31 negative on previous WB		X
		p24 Ag (if p24 Ag negative on index)		X
	Rapid HIV test and counseling		X	
NAT Only Positive	NAT Confirmatory		X	
	p24 Ag		X	
	Viral Load		X	
	Genotyping	Genotyping (in no index sample available)		X
	Drug resistance	Drug resistance (if no index sample available)		X
		NAT confirmatory	X	
		Serology confirmatory	X	
		Viral load	X	
		Western Blot		X
	p24 Ag	X		

Table 2 Planned HBV testing based on index donation test results.

Index Donation Testing Result	Tests to be Conducted on Index Donation Specimens	Tests to be Conducted on Follow-up Samples	SANBS Standard Procedure Testing	REDS-III Study Protocol Testing
Serology Only Positive	Serology (confirmatory)	NAT	X	
	Anti-HBc IgM	Serology (confirmatory)	X	
	Anti-HBs	Anti-HBs	X	
	Anti-HBc Total	Anti-HBc total and IgM	X	
NAT and Serology Concordant Positive	Anti-HBc Total			X
	Viral Load if anti-HBc negative			X
	Genotyping if anti-HBc negative	Genotyping (if no index sample available)		X
		NAT confirmatory		X
		Abbott Prism HBsAg		X
		Viral load		X
		Anti-HBc IgM & Total		X
NAT Only Positive	NAT Confirmatory	NAT Confirmatory	X	
	Abbott Prism HBsAg	Abbott Prism HBsAg	X	
	Viral load	Viral load	X	
	Anti-HBc IgM & Total	Anti-HBc IgM & Total	X	
	Anti-HBs	Anti-HBs	X	
	Genotyping	Genotyping (if no index sample available)		X

### **Procedures for donors with ID NAT yield results**

Blood specimens will be tested at either of the two donation testing centres and the results entered in to the centralized database. Donors will be recruited into the study at the time of return to the blood centre for notification. In addition to the standard tubes collected for confirmation of infection (described below) one 9mL sample will be collected. Once the samples have been collected, the donors will be approached for participation and enrolled into the study. Those interested will undergo a written informed consent process with study staff. Following provision of consent, participants who agree will complete the ACASI research questionnaire. Participants whose confirmatory laboratory results are positive for either incident HIV or incident HBV will be allocated as cases. Participants whose infections are subsequently not confirmed will be excluded from analysis.

If it is not possible to make follow-up notification appointments with the donors at the time of collecting the samples for infection confirmation, follow-up appointments will be made as soon

as the results become available. A similar process will be followed as with the initial letter and telephone contact of the donor.

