#### **Procedures for donors with incident infection identified through LAg Avidity assay (serology and NAT concordant positive, with LAg Avidity results)**

LAg avidity testing will be performed in real time along with routine SANBS supplementary testing and the test results will be available at the time of notification of positive test results. All donors with concordant results, both LAg avidity negative and positive, will initially be counseled in accordance with the SANBS standard procedures which includes the performing of an HIV rapid test when the donor returns for counseling.

The donors with an incident HIV infection identified through the LAg Avidity assay will be assessed for suitability to be enrolled on to the study. If the donor satisfies the inclusion criteria for this study, consent will be sought and the donor enrolled. Blood samples will be collected and the ACASI questionnaire completed.

All other HIV positive donors (serology only and/or non-recent concordant infections) will complete the standard SANBS HIV risk inventory survey as part of the standard SANBS operational procedure.

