#### 4.2.2 Participant Enrollment

##### Modification to Current SANBS Notification Procedures:

All donors with NAT-only infections (HIV, HCV, or HBV) are contacted by letter and telephone to request return to SANBS for additional confirmation of infection. Donors are not informed of the testing results in the letter or during the phone call. Examples of standard notification letters are included (Appendix 1). Currently, all NAT yields are called back to SANBS for follow-up sample collection. SANBS staff does not discuss which virus is suspected based on the NAT yield result. Counseling is done following the testing of the additional samples. A similar letter and approach will be developed and used for persons who are determined to be recently infected based on LAg Avidity testing for HIV and anti-Hepatitis B core negative for HBV.

Currently, donors who test concordant NAT and serology positive for HBV are contacted by telephone if possible and notified of their results with a follow-up letter of the results sent by mail. During the telephone conversation as well as in the letter donors are advised to visit their doctors or local clinic.

Every effort is made to get HIV positive donors back to SANBS for MLO's to do full HIV notification and counseling. Part of this process includes referral to their doctors and/or clinics for further investigation and management. Donors are provided a letter detailing their results which they are urged to take to their doctors.

In order to support the objectives of this study, SANBS will make changes to donor notification procedures:

1. SANBS will seek to inform and counsel all early HBV infections (NAT positive, HBsAg positive or negative and anti-HBc core negative donors) using similar procedures to those used for new HIV infections.
2. SANBS will seek to inform and counsel all of the NAT yields (HIV & HBV). The standard notification letter will be changed to stress that the donor has an early or recently acquired infection. Given the range of testing that is performed on the index donation specimens we expect few notifications to be false positive notifications (See Tables 1 and 2 for standard SANBS index donation testing conducted).
3. All confirmed cases will be urged to seek medical care that conforms to South Africa national treatment guidelines for each infection.

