**Cases Objectives 1 and 2:** The prospective enrollment will build on the existing notification mechanism with additional research nurse staff; we will consent and enroll donors during the retest visit during which they will receive pre-test counseling and be informed of the likelihood of being either HIV or HBV positive (**Consent in Appendix 2**). Following the provision of written informed consent and enrollment, participants will complete the ACASI questionnaire. Although

we plan to administer the ACASI questionnaire immediately following enrollment, we will provide study participants the option of returning to enroll and complete the interview at a later date.

For recent HIV (NAT yield and LAg Avidity recent) and recent HBV (NAT yield and HBsAg positive/anti-HBc negative) infections, all eligible cases will be approached for potential enrollment into the study since we anticipate that no more than 50% of those individuals with a recent infection will return to SANBS for their results following an index donation, but that we will have high success in enrolling these individuals into the study

**Controls:** Controls will be identified from among donors who are negative for all infections for which SANBS screens (HIV, HBV, HCV, and syphilis), and who are stratum-matched by blood centre, age within 5 years, population group. (**Consent in Appendix 3**).

We are proposing on-site recruitment of controls, meaning recruitment of potential controls following successful whole blood donation. To enhance our ability to recruit controls that will be able to be *post-hoc* matched on geographic region, population group, and age, we will select donation sites (both fixed and mobile clinics) with donor characteristics that are similar to donors who are incident HIV-positive. Following completion of the donation, we will invite random donors at predetermined collection sites that have similar demographic characteristics to enrolled cases, to participate in the risk factor study by completing the ACASI. Following completion of testing, donors who are negative for all infections for which SANBS screens will be included in the study.

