**Samples for confirmatory testing.** Blood samples for follow-up testing will be collected in accordance with SANBS standard operating procedures, which place emphasis on identification of the donor and correct labeling of samples to avoid any sample mix-up. Wherever possible, follow-up appointments will be made for the donor to return for the follow-up results at the time of collecting the follow-up samples. Additional sample collection in addition to the standard tubes collected for confirmation will require the additional collection of one 9mL sample. Samples will be labeled, packed and transported according to SANBS standard operating procedures which comply with all local requirements for the transportation of bio-hazardous material. These specimens will be tested at the two donation testing centres and the results entered in to the centralized database.

**Storage of plasma:** While the routine testing is taking place the whole blood donation is processed into a red blood cell (RBC), fresh frozen plasma (FFP) and buffy coat. If any of the screening test results are positive the FFP unit is sent to the National Biorepository housed in Boksburg. If the positive donation is classified as a recent concordant positive the FFP is thawed and three 3.5mL aliquots are sampled and the remaining unit and aliquots are refrozen at -20°C. One aliquot is used to confirm that the blood in the bag is positive, one aliquot is used to determine viral load using the Abbott RT PCR and p24 antigen reactivity using Immunogenetics Innostest mAB in the Virology reference laboratory and one aliquot will be sent to the National Institute of Communicable Diseases (NICD) to have the genotype and drug resistance determined.

A FFP from a donation that is classified as a potential NAT yield will be thawed and the entire product sampled into 3.5 mL aliquots and frozen at -80°C. One aliquot will be sent to the Donation Testing laboratory for replicate testing to eliminate contamination of the index sample. One aliquot will be tested to determine p24 antigen reactivity using the

Immunogenetics mAB Innostest assay and viral load using the Abbott RT PCR assay. One aliquot will be sent to NICD for genotyping and drug resistance. The FFP from a donation classified as a potential serology yield will be thawed and sampled into 3.5mL aliquots and re frozen at -80°C. One aliquot will be sent to Donation Testing for replicate testing to estimate viral load using Probit analysis.

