***If Study Group 3 (A7=3), Skip to Instruction After L9.***

**SECTION L - EXPOSURE AND TREATMENT**

*Study Group 1 Only (A7=1)*

**READ and HEARD:** *This is the final section of the questionnaire. It may be difficult for you to respond to these questions. Again, the responses are anonymous and will help us improve blood safety in South Africa.*

L1. Did you know your HIV status before your donation? (Choose one)

- 0 No
- 1 Yes
- 97 Don't Know
- 98 Refuse to Answer

L2. How do you think you may have become infected with HIV?

-----

L3. When do you think you may have been infected with HIV? (Year)

- \_\_\_\_\_\_ YYYY
- 2097 Don't Know (Year)
- 2098 Refuse to Answer (Year)

L4. When do you think you may have been infected with HIV? (Month) (Choose one)

- January
- February
- March
- April
- May
- June
- July
- August
- September
- October
- November
- December
- Don't Know
- Refuse to Answer

L5. Are you currently taking antiretroviral medicines, also called ARVs? (Choose one)

- 0 No
- 1 Yes skip to L7?
- 97 Don't Know
- 98 Refuse to Answer

L6. Have you taken antiretrovirals (ARVs) in the past? (Choose one)

- 0 No
- 1 Yes
- 97 Don't Know
- 98 Refuse to Answer

L7. (Ask of Women Only) If Female: Did you know you were HIV-positive prior to or during your most recent pregnancy?

- 0 No
- 1 Yes
- 96 Not applicable, never been pregnant **SKIP to After L9.**
- 97 Don't Know
- 98 Refuse to Answer

L8. (Ask of Women Only) Did you take antiretrovirals during your most recent pregnancy to try to prevent HIV transmission to your baby?

- 0 No
- 1 Yes
- 96 Not Applicable
- 97 Don't Know
- 98 Refuse to Answer

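### NAT-yield donors have the extra 9 mL tube drawn before written consent, and those not yet confirmed can be routed to questions that presuppose infection

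*Protocol*

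**What the plan says.** Section 4.2.1, under the procedures for ID-NAT yield donors, describes the retest visit. On the blood draw it says: "In addition to the standard tubes collected for confirmation of infection (described below) one 9mL sample will be collected". The next step is: "Once the samples have been collected, the donors will be approached for participation and enrolled into the study". Interested donors then go through written consent, and those who agree complete the ACASI. Confirmatory results settle afterwards who is a case: "Participants whose infections are subsequently not confirmed will be excluded from analysis".

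Section 4.4.1, on samples for confirmatory testing, again treats the tube as an addition: "Additional sample collection in addition to the standard tubes collected for confirmation will require the additional collection of one 9mL sample".

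The parallel procedure for LAg Avidity cases, also in section 4.2.1, runs the other way: "consent will be sought and the donor enrolled. Blood samples will be collected and the ACASI questionnaire completed". The Objective 3 paragraphs likewise place consent and enrolment before specimens are taken.

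In the paragraph on cases for Objectives 1 and 2 (Participant Enrollment), donors at the retest visit receive pre-test counselling and are to "be informed of the likelihood of being either HIV or HBV positive".

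In Appendix 7, staff enter A7 at the start as HIV case, HBV case or control. Section L is then routed by A7. Group 1 is asked, among other items, "L2. How do you think you may have become infected with HIV", and group 2 is asked the HBV equivalent at L9.

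**The concern.** There are two separate matters, and the first is the weightier.

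**Order of consent.** If the extra tube serves the study, a donor who declines has already given study blood. The NAT-yield procedure does not say what happens to that tube. A consent obtained afterwards does not undo the order of the draw.

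**Section L before confirmation.** A donor recalled so that a screening result can be checked may be asked on a laptop how and when they caught a named virus, while the check is still pending. The protocol itself foresees that some of these participants will not be confirmed. NAT yields and LAg cases would also answer the same items in different states of knowledge, because LAg cases have been counselled first.

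**Working it through.** No sample size, power or alpha figure bears on this point. The check is a reading of the visit sequence, with a count of who meets it.

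**1. Is the 9 mL tube a study tube?** Sections 4.2.1 and 4.4.1 both describe it as beyond the standard confirmation tubes. The protocol gives it no routine purpose. Table 1 lists a follow-up Western blot for NAT-only donors as study testing, and section 4.4.1 stores cells from a 9 mL ACD tube for later studies, so follow-up blood does have research uses. That this particular tube is a study tube remains an inference, because the tube list in section 4.4.1 does not mark which one is the extra.

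**2. Order of steps in the three pathways.**

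| Pathway | Stated order |
|---|---|
| NAT yield (4.2.1) | standard tubes and extra 9 mL, approach, written consent, ACASI, confirmatory result |
| LAg Avidity (4.2.1) | counselling, consent and enrolment, blood, ACASI |
| Objective 3 | consent, enrolment, specimens, ACASI |

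Only the NAT-yield pathway puts the draw before consent.

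**3. How many donors meet that order?** The inputs are about 50 HIV NAT-only infections a year (HIV power section), 40 to 45 true HBV NAT yields a year (HBV power section), three years of enrolment, and about 50% return.
- Per year before return: 50 + 40 = 90, to 50 + 45 = 95.
- Over three years at 50%: 90 × 3 × 0.5 = 135, to 95 × 3 × 0.5 = 142.5.
- Using the HBV return rates in Table 7 instead (12/43 = 28%, or 20/54 = 37% with untyped yields included): 50 × 0.5 + 40 × 0.28 = 36.2 a year, to 50 × 0.5 + 45 × 0.37 = 41.65 a year. Over three years that is 108.6 to 124.95.

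The range is therefore about 109 to 143 donors. The yearly counts cover all of SANBS, and the study runs in five locations, so the true number is likely to be lower. The number who return and then decline is not stated. The protocol expects it to be small.

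**4. Can Section L come before confirmation?** In the NAT-yield procedure the ACASI follows consent, and non-confirmation is described as something found later. The paragraph on cases makes the ACASI immediate by default. A7 offers only HIV case, HBV case or control. The skip rule at K1 and the instruction after K3 read A7 alone. No rule tests whether infection has been confirmed.

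**5. Which items presuppose infection?** L2 to L4 ask how and when the donor was infected with HIV. L7 and L8, for women, assume a positive status or the need to prevent transmission to a baby. L9 assumes HBV infection. L5 and L6, on antiretroviral use, need not presuppose it if worded neutrally.

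**The case against.** The consent point rests partly on material not available for this review. The case consent form is not included, and the purpose of the 9 mL tube is inferred. This stands as a caution, and it is why the tube is called apparently a study tube. It does not change the stated order, which differs from the protocol's own order elsewhere.

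On Section L, four stronger readings are tempting, and the documents do not support them.

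- *Section L tells donors that they are infected.* It does not. Its wording presupposes infection but announces no result. Pre-test counselling comes first, the revised notification letter will already stress an early or recent infection, and questions may be skipped.
- *Every NAT-yield participant is affected.* Section 4.2.1 allows confirmation by viral load, p24 antigen (HIV) or repeat reactivity on index plasma. Table 1 and section 4.4.1 run such tests on the index donation. Few false-positive notifications are expected, and enrolment or the ACASI may take place at a later visit. The problem is confined to donors still unconfirmed when they sit the ACASI.
- *The notification section contradicts itself.* The sentences "SANBS staff does not discuss which virus is suspected based on the NAT yield result. Counseling is done following the testing of the additional samples" describe current practice, which the same section goes on to modify for this study. Telling donors of a likelihood is consistent with the modified procedure.
- *Untyped yields cannot be coded at A7.* In Table 7, 11 of 43 + 11 = 54 yields were untyped (20.4%), as were 8 of the 20 returns (40%). But the footnote says that most untyped yields that confirm are HBV, and index testing adds information. A provisional code is possible.

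It is also fair that Section L has no control comparison and carries no Objective 1 hypothesis, so no stated analysis is damaged. What stands against all this is that none of these provisions moves consent ahead of the extra tube, and none makes Section L conditional on confirmation.

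**Conclusion.** The main point holds: as written, NAT-yield donors give an apparently study-specific 9 mL tube before they are approached and consent, against the order used for LAg cases and Objective 3. It should be corrected before NAT-yield recruitment begins. It would apply to about 109 to 143 returning donors over three years if SANBS-wide counts and the protocol's return rates hold. The serious consequence, study blood from a donor who never consents, falls on the unstated and probably small number who decline.

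The secondary point holds in a limited form: Appendix 7 has no safeguard for NAT yields not yet confirmed from the index donation. Its size cannot be computed, because the documents give no proportion unconfirmed at the time of the ACASI. Both points concern participant protection and the meaning of a few case-only items. Neither affects power or the risk-factor comparison.

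**What to change.** 1. In the NAT-yield procedure of section 4.2.1, obtain written consent before the extra 9 mL tube is drawn. Leave the standard SANBS confirmation tubes where they are. Mark in section 4.4.1 which tube is the extra one.
2. In Appendix 7, keep A7 as a provisional group code so that the K1 skip rule still works. Add a flag for confirmed or not confirmed, and withhold the items that presuppose infection (L2 to L4, L7, L8 and L9) from unconfirmed donors until the confirmatory result has been given.
3. Ask L5 and L6 in neutral wording at the first visit, since antiretroviral use could help in interpreting drug resistance under Objective 2a.

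The first change costs a reordered sentence and a site instruction. The second costs one routing flag and some lost data: the results visit is arranged at the time of sampling only where possible, so donors who do not return will lack the withheld answers, and also L5 and L6 if the third step is not taken.
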